7.5.4 Vital Signs

Analysis set: SAF

The baseline visit is the last measurement taken prior to initial treatment.

Vital signs (systolic blood pressure, diastolic blood pressure, pulse and body temperature) will be summarized using mean, standard deviation, minimum, maximum and median by measurement time point. Additionally, a within-subject change will be calculated per

measurement time point as the post-baseline measurement minus the baseline measurement and summarized by measurement time point.

Tables for potentially clinically significant vital signs will be generated using baseline value and highest value obtained during treatment for each subject for Phase 1 part, Phase 2 part and Phase 1/Phase 2 part totally.

The following potentially clinically significant criteria are defined for each parameter:

Vital Sign Variable	Criteria
SBP	≥180 mmHg AND ≥20 mmHg change from baseline
DBP	≥105 mmHg AND ≥15 mmHg change from baseline
Pulse	≥120 bpm AND ≥15 bpm change from baseline

DBP: Diastolic Blood Pressure; SBP: Systolic Blood Pressure

7.5.5 Electrocardiograms (ECGs)

Analysis set: SAF

The 12-lead ECG will be measured at the scheduled time points. The 12-lead ECGs will be recorded in triplicate (3 separate ECGs, 10 minutes resting prior to first ECG and at least 5 minutes apart per time point) and transmitted electronically for central reading.

ECG variables will be summarized using mean, standard deviation, minimum, maximum and median for each measurement time point, including changes from baseline.

Number and percentage of subjects with normal, not clinically significant abnormal, and clinically significant abnormal results as assessed by investigator for the overall interpretation of 12 lead ECG will be tabulated by measurement time point. A shift analysis table showing shift in overall ECG interpretation from baseline to each time point will be provided. The worst of the three overall ECG interpretations will be used as the time-specific overall ECG interpretation for a subject.

The QT interval corrected for heart rate by Fridericia's formula, QTcF, is defined as: $QTc(F) = QT/(RR)^{0.33}$.

The QTcF interval variables will be summarized by the frequencies of subjects with following categories for each measurement time point.

	QTc Interval Criteria Value (msec)
Normal	≤ 450
Borderline	> 450 to ≤ 480
Prolonged	> 480 to ≤ 500
Clinically significant	> 500

QTc: Corrected Q-T Interval

The change from baseline of QTcF interval variables will be summarized by the frequencies of subjects with following categories for each measurement time point.

Variable	Change from Baseline
QTc Interval (msec)	<0 ≥ 0 to ≤ 30 > 30 to ≤ 60 > 60

QTc: Corrected Q-T Interval

7.5.6 ECOG Performance Status

Analysis set: SAF

Number and percentage of subjects for each category of the ECOG performance status at each assessment time will be provided. Negative change scores indicate an improvement and positive scores indicate a decline in performance.

ECOG scores will also be summarized using shift table from baseline to post-baseline score by visit.

7.6 Analysis of PK

The pharmacokinetic analysis will be performed on the PKAS. For plasma concentrations of ASP2215 and Cytarabine, descriptive statistics will be calculated by time and treatment period.

The PK parameters will be calculated using WinNonlin software (Pharsight Corp, Mountain View, California, US) version 8.0. Non-compartmental methods will be used to derive the values of the PK parameters.

7.6.1 Pharmacokinetic ASP2215 Parameters

The following PK parameters will be estimated in both induction and consolidation period, using plasma concentrations of ASP2215 and actual elapsed times from dosing, provided enough data are available for accurate estimations. Exclusion of PK parameter estimates from the descriptive statistics will be considered by the pharmacokineticist on a case-by-case basis.

[Phase 1 part]

Single dose period: AUC_{24} , AUC_{last} , C_{max} , and t_{max}

[Phase 2 part]

Not applicable.

7.6.2 Change from the Protocol

Note that ASP2215 has a longer half-life (> 24 hours) than the dosing interval thus the following parameters will not be evaluated due to lack of accuracy under the planned PK sampling scheme:

AUC_{inf} , CL/F , λ_z , $t_{1/2}$ and V_z/F

7.7 Analysis of PD

Not applicable for this study except for a subject who was allocated to 40 mg per day. The total concentrations of FLT3 and AXL of the subject will be used only for listings.

7.7.1 Change from the Protocol

Inhibition of FLT3 phosphorylation and inhibition of AXL phosphorylation have not been measured.

7.8 Subgroups of Interest

[Phase 1 part]

For analysis of response variable, subgroup analysis will be conducted using the FAS. Subgroup is defined on the basis of the categorized variables listed below:

Grouping variable	Subgroups
FLT3-ITD Mutation Status	Positive Negative
FLT3-TKD Mutation Status	Positive Negative
FLT3 Mutation Status	Positive Negative

[Phase 2 part]

For primary efficacy analysis and OS analysis, subgroup analysis will be conducted using the TTE-FAS. Subgroups are defined on the basis of the categorized variables listed below:

Grouping variable	Subgroups
Age group	< 65 Years ≥65 Years
Sex	Female Male
Region	Japan Korea Taiwan
FLT3 Mutation Type	FLT3-ITD Mutation Status is positive FLT3-TKD Mutation Status is positive FLT3-ITD Mutation Status and FLT3-TKD Mutation Status are positive

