5.1 Full Analysis Set (FAS)

[Phase 1 part]

Subjects who meet all of the following criteria will be included:

- Received at least 1 dose of study drug
- Assessed for at least 1 efficacy variable after study drug administration

[Phase 2 part]

Subjects who meet all of the following criteria will be included:

- Received at least 1 dose of study drug
- Had at least one post-baseline bone marrow assessment

For the statistical analysis of some Time-to-Event efficacy variables, TTE-FAS will be used. TTE-FAS is defined similarly as the FAS, however, the criterion for bone marrow assessment is removed.

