6.1.2 Primary Efficacy Endpoint

[Phase 1 part]

Not applicable.

[Phase 2 part]

- CR rate after induction therapy period

Defined as the number of subjects who achieve the best response of CR divided by the number of subjects in the analysis population during induction therapy period. Subjects with unknown or missing response, or who provide no information on response will be treated as non-responders and will be included in the denominator when calculating rates.

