7.4 Analysis of Efficacy

[Phase 1 part]

The efficacy analysis will be performed on the FAS.

For response variables, best response after each treatment therapy period will be summarized. The number and percentage of subjects in each category will be presented together with two-sided exact 95% CIs based on binomial distribution. Swimmer's plot will be presented for response variables.

For time-to-event variables efficacy analysis will be summarized using descriptive statistics. The survival curve and the median will be estimated using the Kaplan-Meier method and will be reported along with the corresponding 95% CIs.

[Phase 2 part]

The efficacy analysis will be performed on the FAS and TTE-FAS. The interpretation of statistical results will be based on the FAS. The TTE-FAS will be used to analyze OS and EFS. Analysis of MRD and MR will be performed using MAS.

Primary efficacy variable

For primary efficacy variable, CR rate after induction therapy period, the two-sided 90% exact CI by Clopper-Pearson method will be calculated. The lower limit will be used to compare with the benchmark of CR rate of 55%. The number and percentage of subjects in each category and swimmer's plot will also be presented. As a supportive analysis, CR rate after induction therapy period reported by Day 60 and CR rate after induction therapy period not being dependent on RBC and platelet transfusion (No Transfusion of RBC and Platelet within 1 week prior to disease assessment) will also be calculated.

Other efficacy variables

For other efficacy variables, analysis method will be described as follows:

Categorical variables:

The number and percentage of subjects in each category will be presented together with two-sided exact 95% CIs based on binomial distribution. Swimmer's plot will be presented for response variables.

For response assessment variables, best response rate after each treatment therapy will be summarized. The number and percentage of subjects in each category will be presented together with two-sided exact 95% CIs based on binomial distribution. For subjects who undergo HSCT, any response assessment data after HSCT will not be used (i.e. for those subjects, only response assessment data before HSCT will be used).

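### Phase 2 CR-rate subgroups are placed on the TTE-FAS, while the overall CR rate is by implication on the FAS, so the two can have different denominators

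*SAP*

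**What the plan says.** Three places in the SAP bear on this.

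- **Section 5.1 (Phase 2)** requires for the FAS at least one dose of study drug and this further condition: "Had at least one post-baseline bone marrow assessment". It then introduces the second set and its purpose: "For the statistical analysis of some Time-to-Event efficacy variables, TTE-FAS will be used". The definition follows: "TTE-FAS is defined similarly as the FAS, however, the criterion for bone marrow assessment is removed". The TTE-FAS is thus all treated subjects.
- **Section 7.4 (Phase 2)** names both sets for efficacy and then separates their roles: "The interpretation of statistical results will be based on the FAS. The TTE-FAS will be used to analyze OS and EFS". The paragraph on the primary variable names no set.
- **Section 7.8 (Phase 2)** says: "For primary efficacy analysis and OS analysis, subgroup analysis will be conducted using the TTE-FAS". The subgroups are age group, sex, region and FLT3 mutation type. In the same section, the Phase 1 response subgroups stay on the FAS.

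Section 6.1.2 adds the rule for the primary endpoint when response is missing: "Subjects with unknown or missing response, or who provide no information on response will be treated as non-responders". These subjects remain in the denominator.

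**The concern.** CR rate is not a time-to-event variable and is not among the uses that section 7.4 gives to the TTE-FAS. Section 7.8 nevertheless analyses it there, in a single sentence shared with OS. No reason is given, and no overall CR rate on the TTE-FAS is specified that could link the subgroup tables to the headline.

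A treated subject with no post-baseline marrow would be left out of the overall CR rate but counted as a non-responder in the subgroup tables. The subgroup sizes would then add to more than the primary denominator, and the subgroup rates would pool to less than the reported rate. If missing marrows cluster in one age group or country, that subgroup would look weaker against the headline partly because two different sets are being compared.

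**Working it through.** **The plan's own figure first.** Section 4.1.2 claims more than 80% power with 70 subjects for 70% against 55% at one-sided 0.05. Under the exact binomial rule, which matches a 90% Clopper-Pearson lower limit above 55%, success at n=70 needs at least 46 CRs. The type I error is P(X≥46 | 70, 0.55) = 0.0452 and the power is P(X≥46 | 70, 0.70) = 0.820. The statement reproduces, and this point does not touch it.

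**Inputs.**
- N, subjects treated with study drug (TTE-FAS): 80, assumed equal to the enrolment target in section 4.1.2.
- m, treated subjects without a post-baseline marrow: not in the SAP. Assumed range 0 to 10, where 10 is the gap between 80 enrolled and the 70 used for power.
- x, CR count: 56, which is the planning rate of 70% applied to 80 (0.70 × 80 = 56).

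**Step 1: the numerator does not change.** Section 6.1.1 requires marrow myeloblasts below 5% for CR. A subject without a post-baseline marrow cannot be CR, so x is the same in both sets.

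**Step 2: the denominators.**
- Overall rate on the FAS = x/(N−m).
- Age, sex and region each divide the subjects into non-overlapping groups (assuming everyone is classified), so their TTE-FAS rates pool to Σx_g/Σn_g = x/N.
- Difference = x/(N−m) − x/N = x·m/[N(N−m)]. This is zero at m=0 and positive otherwise.

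**Step 3: numbers, with N=80 and x=56.**

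| m | Overall (FAS) | Pooled subgroups (TTE-FAS) | Difference (percentage points) |
|---|---|---|---|
| 0 | 56/80 = 70.0% | 70.0% | 0 |
| 2 | 56/78 = 71.8% | 70.0% | 1.8 |
| 4 | 56/76 = 73.7% | 70.0% | 3.7 |
| 8 | 56/72 = 77.8% | 70.0% | 7.8 |
| 10 | 56/70 = 80.0% | 70.0% | 10.0 |

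**Step 4: single subgroups.** A subgroup with n_g treated, m_g without marrow and x_g CRs is reported as x_g/n_g. On the FAS it would be x_g/(n_g−m_g). Each subgroup rate is therefore at or below its own FAS value, although one subgroup may still exceed the overall rate.

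**Step 5: mutation type.** Section 7.8 lists ITD positive, TKD positive, and both positive, without saying that they exclude one another. If they overlap, their sizes sum to neither set, so Step 2 is not claimed for this variable.

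**The case against.** - **The TTE-FAS can be defended for CR.** Section 6.1.2 counts subjects with no response information as non-responders, and all treated subjects fit that rule better than a set that requires a marrow. All subgroups share the set, so comparisons between strata are like for like, and the choice cannot inflate any subgroup rate. This stands. It argues for one common set, possibly all treated, and not for two different ones.
- **Primary on FAS is an inference.** The primary-variable paragraph of section 7.4 names no set, and the assignment of the TTE-FAS to OS and EFS does not say that it excludes other uses. This also stands, but the inference is the natural one given "The interpretation of statistical results will be based on the FAS" and "The TTE-FAS will be used to analyze OS and EFS". If the sponsor meant otherwise, section 7.4 needs the correction instead.
- **The gap may be nil.** If every treated subject has a post-baseline marrow, the sets coincide. This is correct, and the point is conditional on m being at least 1.
- **A stronger reading is tempting.** With 5 marrows missing, 49/75 has a lower limit of 55.3% and clears the benchmark, while the same 49 CRs in 80 give 51.5%. A reader might infer that the subgroup tables could overturn the primary result. The SAP does not support this. Section 7.4 compares only the primary CR rate with 55%, and no pooled subgroup rate is tested. The example also uses the smallest successful count: 48/75 has a lower limit of 53.9% and fails on the FAS itself. At 56 CRs the limit clears 55% on either set (64.1% for 56/76, 60.5% for 56/80).

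**Conclusion.** The inconsistency is real and limited. Section 7.8 puts a binary endpoint on a set that section 5.1 defines for time-to-event variables, and sections 7.4 and 5.1 imply that the overall CR rate is on the FAS. If any treated subject lacks a post-baseline marrow, the age, sex and region subgroup CR rates pool to less than the overall rate. On the assumptions above, the gap runs from 0 (m=0) through 3.7 points (m=4) to 10.0 points (m=10). It always runs in that direction, because only the denominator changes.

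The effect is confined to descriptive subgroup tables and to their comparison with the headline. The primary decision, the sample size and the OS subgroups are unaffected. This is a minor consistency point that should be corrected because the correction is so cheap.

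**What to change.** 1. In section 7.8, state that the CR-rate subgroups use the same analysis set as the primary CR analysis, and keep the TTE-FAS for the OS subgroups.
2. In the primary-variable paragraph of section 7.4, name the set used for the primary CR rate.
3. If the primary is moved to all treated subjects, which fits the missing-response rule of section 6.1.2 better, use that set for both the overall rate and the subgroups.

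The cost is one line in each of two sections, with no new data and no change to the methods. If the SAP is not reissued, section 1 already requires changes from the planned analyses to be justified in the CSR, and the change can be recorded there.

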7.9 Other Analyses

7.9.1 FLT3 Mutation Test

[Phase 1 part]

Analysis set: SAF, FAS

The presence/absence of FLT3-ITD mutation status, FLT3-TKD mutation status, FLT3 mutation status and FLT3-ITD mutation status/FLT3-TKD mutation status will be summarized by frequency at each visit.

[Phase 2 part]

Analysis set: SAF, FAS

FLT3 mutation type will be assessed from bone marrow sample taken at the screening visit or at the visit prior to consent. If bone marrow sample is unavailable, the whole blood sample taken at the screening visit will be used. The presence of FLT3-ITD mutation status, FLT3-TKD mutation status and both of them will be summarized by frequency.

7.10 Interim Analysis (and Early Discontinuation of the Clinical Study)

Not applicable.

7.11 Handling of Missing Data, Outliers, Visit Windows, and Other Information

7.11.1 Missing Data

The detail of missing efficacy variable is in Section 6.1.

Missing or partial start and stop dates of adverse events and concomitant medication will be imputed using the following algorithm:

- Imputation rules for partial or missing stop dates:
 - If the month and year are present, then impute as the last day of that month.
 - If only the year is present, impute as December 31 of that year.
 - If the stop date is entirely missing, assume the event or medication is ongoing.
- Imputation rules for partial or missing start dates:

Start Date		Stop Date						missing
		Complete: yyyymmdd		Partial: yyyymm		Partial: yyyy		
		< 1 st dose	≥ 1 st dose	< 1 st dose yyyymm	≥ 1 st dose yyyymm	< 1 st dose yyyy	≥ 1 st dose yyyy	
Partial: yyyymm	= 1 st dose yyyymm	2	1	n/a	1	n/a	1	1
	≠ 1 st dose yyyymm		2	2	2	2	2	2
Partial: yyyy	= 1 st dose yyyy	3	1	3	1	n/a	1	1
	≠ 1 st dose yyyy		3		3	3	3	3
Missing		4	1	4	1	4	1	1

1 = Impute as the date of first dose; 2 = Impute as the first of the month; 3 = Impute as January 1 of the year; 4 = Impute as January 1 of the stop year

The imputed dates will be used to determine whether an AE is/is not treatment emergent. Listings of AEs and concomitant medications will present the actual partial dates; imputed dates will not be shown.

7.11.2 Outliers

All values will be included in the analyses.

7.11.3 LLOQ

- LLOQ for ASP2215

The LLOQ of the plasma sample which was measured by inVentiv is 10 ng/mL when using 0.050 mL of plasma.

As for the plasma sample of P06101 which was measured by ARIA, the LLOQ of the plasma sample is 0.5 ng/mL when using 0.050 mL of plasma.

- LLOQ for Cytarabine

The LLOQ is 0.5 ng/mL when using 0.050 mL of plasma.

7.11.4 BLQ data

Plasma concentrations below the LLOQ will be presented as “<LLOQ” in listings while treated as zero in the analyses.

7.11.5 Visit Windows

[Phase 1 part]

Visit windows are allowed for certain visits per the schedule of assessments. Subject data will not be excluded from analyses due to the subject’s failure to comply with the visit schedule. In the case of multiple observations at a specific visit, the observation which is closest to the target date will be used. If the observations have the same distance to the target visit, the latest one will be used. The baseline visit is the last measurement taken prior to initial treatment.

- Visit Windows for Laboratory Tests

Induction period			
Assessment timing	Scheduled date (Day 1: Day 1 of each cycle Start of treatment)	Acceptable time range	Remarks
Screening	—	7 days before dosing – 1 day before dosing (Before dosing if the screening and Day 1 of Cycle 1 overlap).	Treatment on Day 1 may be started on the day informed consent is obtained when the investigator or subinvestigator judges that immediate treatment is required due to rapid proliferative disease progression. In this case, among the test items specified in both screening and Day 1 of Cycle 1 are not required to be performed twice.
Day 1	Day 1	Before dosing on the scheduled date	Same as above
Day 4	Day 4	Scheduled date	
Day 8	Day 8	Scheduled date	
Day 15	Day 15	Scheduled date ± 1 day	
Day 28	Day 28	Scheduled date ± 7 days	
Day 42	Day 42	Scheduled date + 14 days	
Consolidation period			
Assessment timing	Scheduled date (Day 1: Day 1 of each cycle Start of treatment)	Acceptable time range	Remarks
Day 1	Day 1	Scheduled date	
Day 4	Day 4	Scheduled date	
Day 8	Day 8	Scheduled date	
Day 15	Day 15	Scheduled date – 1 day	
Day 28	Day 28	Scheduled date ± 7 days	
Maintenance period			
Assessment timing	Scheduled date (Day 1: Cycle 1 Day 1 Start of treatment)	Acceptable time range	Remarks
Cycle 1 Day 1	Day 1	Scheduled date	
Cycle X Day 1	Day 28 (X – 1) + 1	Scheduled date ± 3 days	X = Cycle 2 and subsequent cycles

End of treatment (for any period) or at the end of Cycle 26 of the maintenance period	Date of judgment of discontinuation or Cycle 26 Day 28 of the maintenance period	Scheduled date + 7 days	If the scheduled tests at discontinuation have been performed after the final study drug administration, the tests do not have to be repeated even if they were performed before the date of judgment of discontinuation.
---	--	----------------------------	---

● Visit Windows for Vital Signs

Induction period			
Assessment timing	Scheduled date (Day 1: Day 1 of each cycle Start of treatment)	Acceptable time range	Remarks
Screening	—	7 days before dosing –1 day before dosing (Before dosing if the screening and Day 1 of Cycle 1 overlap).	Treatment on Day 1 may be started on the day informed consent is obtained when the investigator or subinvestigator judges that immediate treatment is required due to rapid proliferative disease progression. In this case, among the test items specified in both screening and Day 1 of Cycle 1 are not required to be performed twice.
Day 1	Day 1	Before dosing on the scheduled date	Same as above
Day 8	Day 8	Scheduled date	
Day 15	Day 15	Scheduled date ± 1 day	
Day 28	Day 28	Scheduled date ± 7 days	
Day 42	Day 42	Scheduled date + 14 days	

Consolidation period			
Assessment timing	Scheduled date (Day 1: Day 1 of each cycle Start of treatment)	Acceptable time range	Remarks
Day 1	Day 1	Scheduled date	
Day 8	Day 8	Scheduled date	
Day 15	Day 15	Scheduled date – 1 day	
Day 28	Day 28	Scheduled date ± 7 days	

Maintenance period			
Assessment timing	Scheduled date (Day 1: Cycle 1 Day 1 Start of treatment)	Acceptable time range	Remarks
Cycle 1 Day 1	Day 1	Scheduled date	
Cycle X Day 1	Day 28 (X - 1) + 1	Scheduled date ± 3 days	X = Cycle 2 and subsequent cycles
End of treatment (for any period) or at the end of Cycle 26 of the maintenance period	Date of judgment of discontinuation or Cycle 26 Day 28 of the maintenance period	Scheduled date + 7 days	If the scheduled tests at discontinuation have been performed after the final study drug administration, the tests do not have to be repeated even if they were performed before the date of judgment of discontinuation.

- Visit Windows for 12-lead ECG (Including assessment of QT interval)

Induction period			
Assessment timing	Scheduled date (Day 1: Day 1 of each cycle Start of treatment)	Acceptable time range	Remarks
Screening	—	7 days before dosing – 1 day before dosing (Before dosing if the screening and Day 1 of Cycle 1 overlap).	QT interval assessments will not be performed at the central ECG laboratory
Day 1 pre-dose	Day 1	Scheduled date, within 30 minutes before dosing	Performed prior to PK blood sampling
Day 4 pre-dose	Day 4	Scheduled date, within 30 minutes before dosing	
Day 4 4 hours post-dose	Day 4	Scheduled date, within \pm 30 minutes of the scheduled time	
Day 11 pre-dose	Day 11	Scheduled date, within 30 minutes before dosing	
Day 17 pre-dose	Day 17	Scheduled date – 1 day, within 30 minutes before dosing	
Day 17 4 hours post-dose	Day 17	Scheduled date – 1 day, within \pm 30 minutes of the scheduled time	
Day 28	Day 28	Scheduled date \pm 7 days	
Day 28	Day 28	Scheduled date \pm 7 days	
Consolidation period			
Assessment timing	Scheduled date (Day 1: Day 1 of each cycle Start of treatment)	Acceptable time range	Remarks
Day 1 pre-dose	Day 1	Scheduled date, within 30 minutes before dosing	Performed prior to PK blood sampling
Day 1 4 hours post-dose	Day 1	Scheduled date, within \pm 30 minutes of the scheduled time	
Day 2 pre-dose	Day 2	Scheduled date, within 30 minutes before dosing	
Day 15	Day 15	Scheduled date – 1 day	Performed prior to PK blood sampling. If performed on Day 14 within the allowed visit window [-1] for Day 15, 12-lead ECG will be performed at pre-dose.
End of treatment (for any period) or at the end of Cycle 26 of the maintenance period	Date of judgment of discontinuation or Cycle 26 Day 28 of the maintenance period	Scheduled date + 7 days	QT interval assessments will not be performed at the central ECG laboratory. If the scheduled tests at discontinuation have been performed after the final study drug administration, the tests do not have to be repeated even if they were performed before the date of judgment of discontinuation.

ECG: Electrocardiogram

● Visit Windows for ECOG Performance Status

Induction period			
Assessment timing	Scheduled date (Day 1: Day 1 of each cycle Start of treatment)	Acceptable time range	Remarks
Screening	—	7 days before dosing – 1 day before dosing (Before dosing if the screening and Day 1 of Cycle 1 overlap).	Treatment on Day 1 may be started on the day informed consent is obtained when the investigator or subinvestigator judges that immediate treatment is required due to rapid proliferative disease progression. In this case, among the test items specified in both screening and Day 1 of Cycle 1 are not required to be performed twice.
Day 1	Day 1	Before dosing on the scheduled date	Same as above
Day 8	Day 8	Scheduled date	
Consolidation period			
Assessment timing	Scheduled date (Day 1: Day 1 of each cycle Start of treatment)	Acceptable time range	Remarks
Day 1	Day 1	Scheduled date	
Day 8	Day 8	Scheduled date	
Maintenance period			
Assessment timing	Scheduled date (Day 1: Cycle 1 Day 1 Start of treatment)	Acceptable time range	Remarks
Cycle 1 Day 1	Day 1	Scheduled date	
End of treatment (for any period) or at the end of Cycle 26 of the maintenance period	Date of judgment of discontinuation or Cycle 26 Day 28 of the maintenance period	Scheduled date + 7 days	If the scheduled tests at discontinuation have been performed after the final study drug administration, the tests do not have to be repeated even if they were performed before the date of judgment of discontinuation.

● Visit Windows for ECHO or MUGA

Assessment timing	Scheduled date	Acceptable time range	Remarks
Screening	—	7 days before dosing – 1 day before dosing (Before dosing if the screening and Day 1 of Cycle 1 overlap).	To be performed on patients with a history of congestive heart failure of NYHA class 3 or 4 (however, not necessary to be repeated at screening if ECHO or MUGA performed within 3 months prior to enrollment showed LVEF of $\geq 45\%$).

ECHO: Echocardiogram; MUGA: Multiple Gate Acquisition; NYHA: New York Heart Association; LVEF: Left Ventricular Ejection Fraction

● Visit Windows for Chest X-Ray or Chest CT

Assessment timing	Scheduled date	Acceptable time range	Remarks
Screening	—	7 days before dosing – 1 day before dosing (Before dosing if the screening and Day 1 of Cycle 1 overlap).	

Chest X-ray or chest CT at screening is not necessary if either was performed within 7 days before study enrollment even before obtaining consent. During any treatment period, chest X-ray or chest CT will be performed whenever it is determined to be clinically necessary based on the subject's clinical conditions.

● Visit Windows for Body Height/Weight

Induction period			
Assessment timing	Scheduled date (Day 1: Day 1 of each cycle Start of treatment)	Acceptable time range	Remarks
Screening	—	7 days before dosing – 1 day before dosing (Before dosing if the screening and Day 1 of Cycle 1 overlap).	Height is measured only at screening. Treatment on Day 1 may be started on the day informed consent is obtained when the investigator or subinvestigator judges that immediate treatment is required due to rapid proliferative disease progression. In this case, among the test items specified in both

			screening and Day 1 of Cycle 1 are not required to be performed twice.
Day 1	Day 1	Before dosing on the scheduled date	Same as above
Consolidation period			
Assessment timing	Scheduled date (Day 1: Day 1 of each cycle Start of treatment)	Acceptable time range	Remarks
Day 1	Day 1	Scheduled date	
Maintenance period			
Assessment timing	Scheduled date (Day 1: Cycle 1 Day 1 Start of treatment)	Acceptable time range	Remarks
Day 1	Day 1	Scheduled date	
End of treatment (for any period) or at the end of Cycle 26 of the maintenance period	Date of judgment of discontinuation or Cycle 26 Day 28 of the maintenance period	Scheduled date + 7 days	If the scheduled tests at discontinuation have been performed after the final study drug administration, the tests do not have to be repeated even if they were performed before the date of judgment of discontinuation.

- Visit Windows for Pregnancy Test (for WOCBP)

Induction period			
Assessment timing	Scheduled date	Acceptable time range	Remarks
Screening	—	7 days before dosing – 1 day before dosing (Before dosing if the screening and Day 1 of Cycle 1 overlap).	
Consolidation period			
Assessment timing	Scheduled date (Day 1: Day 1 of each cycle Start of treatment)	Acceptable time range	Remarks
Day 1	Day 1	Scheduled date	
Maintenance period			
Assessment timing	Scheduled date (Day 1: Cycle 1 Day 1 Start of treatment)	Acceptable time range	Remarks
Cycle 1 Day 1	Day 1	Scheduled date	
End of treatment (for any period) or at the end of Cycle 26 of the maintenance period	Date of judgment of discontinuation or Cycle 26 Day 28 of the maintenance period	Scheduled date + 7 days	If the scheduled tests at discontinuation have been performed after the final study drug administration, the tests do not have to be repeated even if they were performed before the date of judgment of discontinuation.

- Visit Windows for Bone Marrow Tests (Bone Marrow Aspiration or Biopsy)

Induction period			
Assessment timing	Scheduled date (Day 1: Day 1 of each cycle Start of treatment)	Acceptable time range	Remarks
Screening	—	7 days before dosing – 1 day before dosing (Before dosing if the screening and Day 1 of Cycle 1 overlap).	Not necessary to repeat if the test was performed within 28 days prior to study enrollment even before obtaining consent.
Day 28	Day 28	Scheduled date ± 7 days	
Consolidation period			
Assessment timing	Scheduled date (Day 1: Day 1 of each cycle Start of treatment)	Acceptable time range	Remarks
Day 1	Day 1	Scheduled date – 7 days	Performed only at the start of Cycle 1 of consolidation period
Maintenance period			
Assessment timing	Scheduled date (Day 1: Cycle 1 Day 1 Start of treatment)	Acceptable time range	Remarks
Cycle 1 Day 1	Day 1	Scheduled date – 7 days	
End of treatment (for any period) or at the end of Cycle 26 of the maintenance period	Date of judgment of discontinuation or Cycle 26 Day 28 of the maintenance period	Scheduled date + 7 days	If the scheduled tests at discontinuation have been performed after the final study drug administration, the tests do not have to be repeated even if they were performed before the date of judgment of discontinuation.

During the maintenance period, the bone marrow test will be performed whenever it is determined to be clinically necessary.

- Visit Windows for Plasma PK Assessment for ASP2215 and Cytarabine

Induction period			
Assessment timing	Scheduled date (Day 1: Cycle 1 Day 1 Start of treatment)	Acceptable time range	Remarks
Cycle 1 Day 1 pre-dose	Day 1	Scheduled date, within 30 minutes before dosing	Blood sampling for cytarabine
Cycle 1 Day 3 pre-dose	Day 3	Scheduled date, within 30 minutes before dosing	Blood sampling for cytarabine
Cycle 1 Day 4 pre-dose	Day 4	Scheduled date, within 30 minutes before dosing	Blood sampling for ASP2215
Cycle 1 Day 4 1 hour post-dose	Day 4	Scheduled date, scheduled time \pm 10 minutes	
Cycle 1 Day 4 2 hours post-dose	Day 4	Scheduled date, scheduled time \pm 10 minutes	
Cycle 1 Day 4 4 hours post-dose	Day 4	Scheduled date, scheduled time \pm 20 minutes	
Cycle 1 Day 4 6 hours post-dose	Day 4	Scheduled date, scheduled time \pm 20 minutes	
Cycle 1 Day 4 10 hours post-dose	Day 4	Scheduled date, scheduled time \pm 20 minutes	
Cycle 1 Day 4 24 hours post-dose	Day 5	Scheduled date, scheduled time \pm 60 minutes and prior to Day 5 dosing	
Cycle 1 Day 8 pre-dose	Day 8	Scheduled date, within 30 minutes before dosing	
Cycle 1 Day 11 pre-dose	Day 11	Scheduled date, within 30 minutes before dosing	Blood sampling for ASP2215
Cycle 1 Day 17 pre-dose	Day 17	Scheduled date – 1 day, within 30 minutes before dosing	
Cycle 1 Day 28	Day 28	Scheduled date \pm 7 days	

Consolidation period			
Assessment timing	Scheduled date (Day 1: Cycle 1 Day 1 Start of treatment)	Acceptable time range	Remarks
Cycle 1 Day 1 pre-dose	Day 1	Scheduled date, within 30 minutes before dosing	Blood sampling for ASP2215
Cycle 1 Day 1 1 hour post-dose	Day 1	Scheduled date, scheduled time \pm 10 minutes	
Cycle 1 Day 1 2 hours post-dose	Day 1	Scheduled date, scheduled time \pm 10 minutes	
Cycle 1 Day 1 4 hours post-dose	Day 1	Scheduled date, scheduled time \pm 20 minutes	
Cycle 1 Day 1 6 hours post-dose	Day 1	Scheduled date, scheduled time \pm 20 minutes	
Cycle 1 Day 1 10 hours post-dose	Day 1	Scheduled date, scheduled time \pm 20 minutes	
Cycle 1 Day 1 24 hours post-dose	Day 2	Scheduled date, scheduled time \pm 60 minutes and prior to Day 2 dosing	Blood sampling for ASP2215 and cytarabine
Cycle 1 Day 6 pre-dose	Day 6	Scheduled date, within 30 minutes before dosing	
Cycle 1 Day 15	Day 15	Scheduled date - 1 day	Blood sampling for ASP2215. If performed on Day 14 within the allowed visit window [-1] for Day 15, blood sampling will be performed at pre- dose.
End of treatment (for any period)	Date of judgment of discontinuation	Scheduled date + 7 days	Blood sampling for ASP2215 is strongly recommended if possible

Both in the induction and consolidation periods, blood sampling for PK analysis is performed only during Cycle 1.

- Visit Windows for FLT3 Mutation Test

Induction period			
Assessment timing	Scheduled date	Acceptable time range	Remarks
Screening	—	7 days before dosing – 1 day before dosing (Before dosing if the screening and Day 1 of Cycle 1 overlap).	
Consolidation period			
Assessment timing	Scheduled date (Day 1: Cycle 1 Day 1 Start of treatment)	Acceptable time range	Remarks
Cycle 1 Day 1	Day 1	Scheduled date + 7 days	Performed only for Cycle 1 of consolidation period
Maintenance period			
Assessment timing	Scheduled date (Day 1: Cycle 1 Day 1 Start of treatment)	Acceptable time range	Remarks
Cycle 1 Day 1	Day 1	Scheduled date	

[Phase 2 part]

All analyses except for the analysis based on central laboratory data will be based on CRF visit except for the baseline. The baseline visit is the last measurement taken prior to initial treatment.

For the analysis based on central laboratory data, visit windows are allowed for certain visits per the schedule of assessments. Subject data will not be excluded from analyses due to the subject's failure to comply with the visit schedule. The visit windows for assessments are described in the following table.

CRF visit	Visit Window
Induction Day 8	Scheduled day
Induction Day 15	D15 ± 2
Induction Day 21	D21 ± 2
Induction Day 28	D28 + 7
Induction Day 42	D42 + 7
Induction Day 56	D56 + 7
Consolidation Day 8	Scheduled day
Consolidation Day 15	D15 ± 2
Consolidation Day 21	D21 + 7
Maintenance Cycle 2 Day 1	(Maintenance Cycle 1 Day 1+28) ± 7
Maintenance Cycle 5 Day 1	(Maintenance Cycle 1 Day 1+112) ± 7
Maintenance Cycle 8 Day 1	(Maintenance Cycle 1 Day 1+196) ± 7
Maintenance Cycle 11 Day 1	(Maintenance Cycle 1 Day 1+280) ± 7
Maintenance Cycle 14 Day 1	(Maintenance Cycle 1 Day 1+364) ± 7
Maintenance Cycle 17 Day 1	(Maintenance Cycle 1 Day 1+448) ± 7
Maintenance Cycle 20 Day 1	(Maintenance Cycle 1 Day 1+532) ± 7
Maintenance Cycle 23 Day 1	(Maintenance Cycle 1 Day 1+616) ± 7
Maintenance Cycle 26 Day 1	(Maintenance Cycle 1 Day 1+700) ± 7

In the case of multiple observations at a specific visit, the observation which is closest to the target date will be used. If the observations have the same distance to the target visit, the latest one will be used. The baseline visit is the last measurement taken prior to initial treatment. If more than one observation is made on the same day, an average value if continuous or the worst value if categorical will be included in the analysis.

